### 12.3 Sample Size

A total sample size of 222 subjects was selected for the study. Assuming the true mean difference between pre-op and 24 month follow-up VAS is 3.66 and the standard deviation is 2.0, a sample size of 189 subjects provides >87% power to detect a statistically significant difference between the mean post-op VAS and the OPC of 3.25 using a one-sided one-sample t-test at a significance level of 0.05. In order to account for approximately 15% attrition, based on clinical experience, 222 subjects will be enrolled.

### 12.4 Analysis Populations

Analysis Populations are defined as follows:

- The Intent-to-Treat (ITT) population includes all enrolled subjects.
- The Per-Protocol population includes all enrolled subjects who have no major protocol violations (defined as not meeting inclusion/exclusion criteria or not being consented properly) and have 24 month VAS scores.

The effectiveness analysis will be performed on the Per Protocol population. Analysis of the ITT population considering several missing data imputations will be confirmatory of the Per Protocol analysis. Safety summaries will be performed on the ITT population.

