## 8 STUDY ENROLLMENT/EVALUATIONS

### 8.1 Patient Screening and Enrollment

Consecutive patients who potentially meet the study inclusion and exclusion criteria will be screened for eligibility. Diagnostic imaging studies to confirm the diagnosis of DDD with up to Grade 1 spondylolisthesis between and including the levels of L2-S1, must be completed within 180 days of the planned date of surgery (provided there have been no significant changes in the patient's clinical presentation). If, at an interim point following the initial imaging, and prior to surgery, the subject experiences a significant change in his/her clinical presentation, the changes should be documented and the images repeated. Patients will be screened as follows:

- Consecutive patients are potentially eligible for entry into the study based on their age and whether their medical condition appears to generally fit the characteristics specific to this study.
- Patients who agree to enter the study must sign the approved informed consent form.
- A patient is considered enrolled in the study after signing the IRB/EC approved informed consent. Consented patients complete the remainder of the screening process to confirm study eligibility. Patients who do not fulfill the screening criteria are considered Screening Failures and will be documented on the Screening & Enrollment Log. Screening failures will not count against the total number of subjects eligible for analysis.
- Subjects who have signed the informed consent and fulfilled the Inclusion/Exclusion criteria are then scheduled for surgery. It is important that surgery be scheduled within 90 days from the date that the subject completed the required pre-operative questionnaires for the study and within 180 days from the date of the required pre-operative X-rays (provided there have been no significant changes in the patient's clinical presentation). The following should be considered when evaluating whether or not the change in clinical presentation is considered significant: an increase in related pain of approximately 3 points (on VAS scale from 0-10), a change in the location of the pain, deteriorating neurological status or other conditions where repeat radiographic studies may be necessary. The objective is to ensure that the patient still meets the eligibility criteria based on the medical judgment of the surgeon.

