### 8.3 Hospitalization/Surgery/Discharge

Subjects will be admitted to the hospital according to the Investigator's standard for non-cervical spine surgery. Prophylactic antibiotics may be administered prior to surgery in accordance with the surgeon's standard of care and anesthesia will be administered per standard operating procedures. The device will be implanted in accordance with methods detailed in the instructions for use for the respective device systems.

Data points required on the Operative case report form must be documented at the time of surgery. Intra-operative adverse events must be recorded.

A Subject may be excluded from the study intra-operatively at the discretion of the Investigator if unexpected findings/occurrences dictate deviation from the intended study procedure. Justification for an intra-operative exclusion and alternative surgical procedure must be fully documented in the subject's medical record and on the Study Exit case report form. A subject who is excluded intra-operatively will be considered an overall treatment failure.

If the patient experienced an adverse event(s) during the hospitalization it should be documented and recorded on an Adverse Event case report form. The subject may be instructed to return to normal activity at the discretion of the Investigator.

Additional post-operative restrictions may be imposed according to the standard of care normally utilized by the Investigator. In addition, subjects should be instructed to notify the Investigator if experiencing untoward events including but not limited to noticeable pain, numbness, tingling, or weakness that does not decrease with rest, swelling of the lower extremities that does not decrease, or increased pain, erythema, edema or drainage from the surgical incision. The Investigator should then determine if an evaluation is warranted.

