## 9 ADVERSE EVENTS

### 9.1 Definitions

#### 9.1.1 Adverse Event

An Adverse Event (AE) is defined as any untoward medical occurrence in a subject undergoing surgery in this trial which does not necessarily have a causal relationship with this intervention. An AE can, therefore, be any unfavorable and unintended sign (including an abnormal laboratory finding), symptom, or disease temporally associated with the use of the one of the devices, whether or not the event is considered causally related to the use of the device. Any worsening of a pre-existing condition or illness is considered an AE. Laboratory abnormalities and changes in vital signs are considered to be AEs only if they result in discontinuation from the study, necessitate therapeutic medical intervention, and/or if the Investigator considers them to be AEs.

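### The safety denominator is the consent-based ITT set, so eligible subjects who are never operated on stay in it and modestly dilute surgical complication rates

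*Combined protocol and SAP*

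**What the plan says.** Section 12.4 defines two analysis sets, ITT and Per Protocol. On the first it says "The Intent-to-Treat (ITT) population includes all enrolled subjects", and on safety it says "Safety summaries will be performed on the ITT population". It defines no treated set or safety set.

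Section 8.1 fixes the moment of enrolment: "A patient is considered enrolled in the study after signing the IRB/EC approved informed consent". Eligibility is settled afterwards: "Consented patients complete the remainder of the screening process to confirm study eligibility". Those who fail are dealt with in one sentence: "Screening failures will not count against the total number of subjects eligible for analysis". Those who pass are scheduled for surgery, and the interval may be long: "It is important that surgery be scheduled within 90 days from the date that the subject completed the required pre-operative questionnaires". Section 8.10 lets a subject withdraw consent at any time.

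Section 8.3 covers exclusion on the operating table: "A subject who is excluded intra-operatively will be considered an overall treatment failure". It does not say how such a subject enters the safety tables.

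The comparator in 4.3 is literature patients in whom the XLIF system was used, so operated patients only. The synopsis objective and section 2.1 set RAVINE complication incidence against those published results. Section 12.6 plans descriptive incidence tables at each follow-up interval, with no test, margin or literature complication rate.

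**The concern.** Read together, 12.4 and 8.1 give a safety denominator that is not limited to operated patients. A subject who consents, meets the criteria and then leaves before surgery is not a screening failure and remains in ITT. The plan recognises that enrolled, unoperated subjects exist: section 11.3 allows the first monitoring visit, timed after the first 2 to 5 enrolments, to take place before the first surgery.

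Such a subject adds one to the denominator of the revision, removal and surgical complication rates and can add nothing to the numerator. The published rates have no such members. For these events the difference runs in one direction only, towards a lower RAVINE rate. Because safety is reported descriptively, the tabulated percentage is itself what a reader will compare with the literature.

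**Working it through.** **Inputs from the documents**
- Safety set: ITT, all enrolled subjects (12.4). Enrolment: at consent (8.1).
- Screening failures: not counted (8.1); 12.4 is silent.
- Control: operated XLIF patients (4.3).
- Sample size: 222 enrolled, 189 evaluable, about 15% attrition (12.3).

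**Inputs assumed, because the documents give none**
- u, the share of the ITT set never operated on: 2% to 10%.
- r, the surgical complication rate among operated subjects: 20% or 30%, for illustration.

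**Step 1: the plan's own figures.** 189 / 0.85 = 222.4, which agrees with 222. The allowance for all losses is 222 - 189 = 33 subjects, or 33 / 222 = 14.9%. The plan states no safety rate or safety sample size, so there is no safety figure to reproduce. The attrition allowance does help to bound u.

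**Step 2: who remains in the denominator.**

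| Subject | In ITT as written? | Can have a surgical complication? |
|---|---|---|
| Consented, fails criteria | Apparently not (8.1), but 12.4 does not say so | No |
| Eligible, leaves before surgery | Yes | No |
| Excluded intra-operatively | Yes | Yes |
| Operated with the study system | Yes | Yes |

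The second row is the problem.

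**Step 3: size.** If unoperated subjects contribute no surgical complications, the reported rate is r x (1 - u).

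| u | Subjects of 222 | r = 20% | r = 30% |
|---|---|---|---|
| 2% | 4 | 0.20 x 0.98 = 19.6% | 0.30 x 0.98 = 29.4% |
| 5% | 11 | 0.20 x 0.95 = 19.0% | 0.30 x 0.95 = 28.5% |
| 10% | 22 | 0.20 x 0.90 = 18.0% | 0.30 x 0.90 = 27.0% |

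**Step 4: plausible range.** At u = 10%, 22 of the 33 allowed losses occur before surgery, leaving 11 for two years of follow-up. At u = 15% (33 subjects) the whole allowance is used. Shares that high do not fit the plan's own expectation.

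**Step 5: against sampling error.** The 95% half-width at n = 222 is 1.96 x sqrt(r(1 - r) / 222). This is 5.3 points at r = 20% and 6.0 points at r = 30%. The shifts in step 3 are 0.4 to 2.0 points and 0.6 to 3.0 points, so they are smaller than the sampling error. Unlike sampling error, they always have the same sign.

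**The case against.** The best counter-argument is that other sections point to a treated denominator. Section 4.2 describes the treatment group as patients treated with RAVINE. Section 9.1.1 defines an adverse event as "any untoward medical occurrence in a subject undergoing surgery in this trial". Follow-up visits are timed from the procedure (8.4), so an unoperated subject has no follow-up interval, and 12.6 does not say which denominator each interval uses. On this view the plan only needs its definitions reconciled. Part of that stands: if the interval tables count only subjects followed to that interval, the dilution there largely disappears. But none of these sections overrides the explicit rule in 12.4, and that rule is the one a programmer would follow.

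A reader might also infer more than the documents support:
- *That everyone who signed consent is in the denominator.* The sentence on screening failures in 8.1 most naturally removes those who fail the criteria.
- *That subjects delayed beyond the 90-day window are unoperated.* Section 8.1 calls the timing important. It does not say that a late subject goes without surgery.
- *That intra-operative exclusions dilute the rate.* They were taken to surgery, can have complications and belong in the denominator.
- *That a trial decision is biased.* The primary endpoint is VAS (6.1, 12.2), the literature tables in 12.2 hold only VAS results, and 12.6 is descriptive.

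**Conclusion.** The point holds in a limited form. As written, safety rates are computed on a set that includes eligible subjects who never had surgery, and this lowers surgical complication, revision and removal rates relative to a control made up of operated patients. That is the comparison named in the synopsis and in 2.1.

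Under the assumed 2% to 10% not operated on, the reported rate is 98% to 90% of the rate among operated subjects. The conclusion on direction rests on 12.6 using the full ITT denominator and on unoperated subjects having no surgical complications. It does not extend unchanged to the overall adverse event rate, because events are recorded from the pre-operative visit (8.2.1, 8.6.1, 9.2) and an unoperated subject may have one. The effect is probably modest and touches no hypothesis test. It is still worth correcting, because the direction is fixed and the correction is cheap.

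**What to change.** In 12.4, define a safety population of all subjects in whom the study procedure was started, including those excluded intra-operatively. In 12.6, name it as the denominator for the adverse event, serious adverse event, revision and removal rates, and say how the denominator is formed at each follow-up interval. State in 12.4 that screening failures are outside ITT, so that it agrees with 8.1.

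Report subjects who consented but were not operated on in the disposition table, together with a separate listing of any adverse events they had before exit. Without that listing, their recorded events would drop out of the safety report.

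The cost is a few sentences and one short listing. No new data are needed: the surgery date is collected under 8.3.1, and withdrawals are recorded on the Study Exit form under 8.10. Reported rates become slightly less favourable to the device.

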### 12.5 Analysis of Primary Endpoint

The primary effectiveness endpoint will be evaluated on the Per Protocol population by a one-sided one-sample t-test of the RAVINE system which is measured as the difference between the pre-op and 24 month post-op Back VAS and the Leg VAS as compared to 3.25, the literature reported differences.

As secondary analyses, the comparison of the difference between the pre-op and 24 month Back VAS and Leg VAS will be repeated as follows:

- Considering ITT subjects with available 12 or 24 month data only. In the event that a subject has 12 month data but no 24 month data, the 12 month VAS scores will be used. Subjects without 12 or 24 month VAS measurements will be excluded.
- A Last Observation Carried Forward (LOCF) approach for all ITT subjects

### 12.6 Safety Analyses

Incidence rates of adverse events will be provided descriptively in tabular form for each study group for the overall adverse event rate, serious adverse event rates, revision rates, removal rates, etc. at each follow-up interval.

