#### 7.4 Study Duration

Study subjects will be expected to participate in this study for 24 months following surgery, with follow-up evaluations at initial post-op, 3 months, 6 months, 12 months, and 24 months.

CONFIDENTIAL DO NOT COPY

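### Section 12.6 puts safety rates on the all-enrolled ITT set with no at-risk denominator or censoring rule; if all ITT subjects are the divisor, later re-intervention and SAE rates come out somewhat low

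*Combined protocol and SAP*

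**What the plan says.** Section 12.6 is a single sentence. It states that "Incidence rates of adverse events will be provided descriptively in tabular form for each study group", and the measures listed are the "overall adverse event rate, serious adverse event rates, revision rates, removal rates, etc. at each follow-up interval". It does not give the divisor for an interval, and it does not say whether the rates are cumulative or interval-specific.

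The only population rule is in Section 12.4: "Safety summaries will be performed on the ITT population". The same section defines the set: "The Intent-to-Treat (ITT) population includes all enrolled subjects". Section 8.1 dates enrolment from consent ("A patient is considered enrolled in the study after signing the IRB/EC approved informed consent"), with the qualification that "Screening failures will not count against the total number of subjects eligible for analysis".

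On follow-up, Section 7.4 says "Study subjects will be expected to participate in this study for 24 months following surgery". Section 12.3 expects some loss: "In order to account for approximately 15% attrition, based on clinical experience, 222 subjects will be enrolled".

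Nowhere in Section 12 is there a number at risk, a person-time rate, a censoring rule or a time-to-event estimate for safety.

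**The concern.** Further surgery at the operative site is one of the primary safety objectives in Section 5.2. The synopsis and Section 4.1 say that complications will be set against published XLIF results. The safety tables therefore carry a main message of the study, even though they are descriptive.

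If each rate is a count divided by all ITT subjects, someone who leaves at month 6 remains in the 12–24 month denominator, but an event after month 6 cannot be recorded. Compared with complete follow-up of the same subjects, this can only lower the count. The shortfall grows with time since surgery. With no concurrent arm, there is no control group in which the same loss would occur and offset it.

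If division by all ITT subjects is not intended, the divisor of a primary safety result is still open and could be chosen after the data are seen.

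**Working it through.** **The plan's own figures.** 222 × 0.85 = 188.7, which agrees with the 189 evaluable subjects in Section 12.3; (222 − 189)/222 = 14.9%, or 33 subjects. (189/0.85 = 222.4 would round up to 223, within the plan's stated approximation.) The stated power also reproduces: a one-sided one-sample t-test with n = 189, difference 3.66 − 3.25 = 0.41, SD 2.0 and alpha 0.05 gives 87.8% by the noncentral t, against more than 87% in the plan. No safety rate or safety precision is stated, so there is no safety figure to reproduce.

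**Inputs for the illustration**
- Attrition D = 15% by 24 months (Section 12.3), also varied to 10% and 25%.
- True 24-month event risk F = 5%, 10%, 15%. These are assumptions; the documents give none.
- Constant event and drop-out hazards, independent of each other (assumption).
- Fixed divisor of all ITT subjects (the reading under test).

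**Formulas.** λ = −ln(1 − F)/24 and μ = −ln(1 − D)/24 per month.
- Rate shown at 24 months = λ/(λ + μ) × [1 − (1 − F)(1 − D)].
- Rate shown for 12–24 months = λ/(λ + μ) × [√((1 − F)(1 − D)) − (1 − F)(1 − D)].
- True 12–24 month increment = √(1 − F) − (1 − F).

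**Worked case, F = 10%, D = 15%.** λ/(λ + μ) = 0.10536/(0.10536 + 0.16252) = 0.3933, and (1 − F)(1 − D) = 0.765.
- 24 months: 0.3933 × 0.235 = 9.2%, against 10%.
- 12–24 months: 0.3933 × (0.8746 − 0.765) = 4.3%, against 0.9487 − 0.9 = 4.9%.

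**Results at 15% attrition**

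| True 24-month risk | Shown | Relative | True 12–24 month increment | Shown | Relative |
|---|---|---|---|---|---|
| 5% | 4.6% | −7.6% | 2.5% | 2.2% | −11.4% |
| 10% | 9.2% | −7.6% | 4.9% | 4.3% | −11.4% |
| 15% | 13.9% | −7.5% | 7.2% | 6.4% | −11.4% |

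**Sensitivity at a true 10%.** With 10% attrition the 24-month rate shows as 9.5% (5% low) and the late increment as 4.5% (8% low). With 25% attrition they show as 8.7% (13% low) and 3.9% (19% low). The bound at 15% attrition, if all drop-out came before all events, is 10% × 0.85 = 8.5%.

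**Scale.** At a true 10%, 222 subjects would give 22.2 events with full follow-up and 20.5 recorded. The 95% half-width is 1.96 × √(0.1 × 0.9/222) = 3.9 percentage points, so a bias of about 0.8 points is roughly one fifth of it.

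**What an at-risk divisor does.** The fraction still under follow-up at 12 months is √0.85 = 0.922. Dividing by it gives 0.0431/0.922 = 4.7%, about 4% low instead of 11%. A Kaplan-Meier estimate removes the remainder when drop-out is unrelated to event risk.

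**The case against.** The strongest reply is that the plan does not state the method being criticised. Section 12.6 speaks of incidence rates and Section 12.4 names a population; neither fixes the divisor at each interval. A table on the ITT set showing the number still followed would comply. Section 12.5 even uses ITT subjects with available data for one VAS analysis, so ITT is not always a fixed number. This stands: a reader might infer that the plan prescribes crude percentages and counts leavers as event-free, and the documents do not say so. Section 12.5 also cuts the other way, though. Where subjects without data are to be left out, the plan says so, and it says nothing similar for safety.

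Second, the 15% is an allowance for the 24-month VAS test, not a forecast of lost adverse-event follow-up. Events are monitored continuously, unscheduled visits are recorded, and Section 8.9 requires two calls and a certified letter before a subject counts as lost. Unobserved time may be shorter than assumed. This also stands, and is why the figures are only an illustration.

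Third, the effect is small and no safety test, margin or success criterion uses it. Correct; it limits the weight of the point without removing it.

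Fourth, a reader might infer that the comparison with the literature must favour the device. That depends on how the published rates were calculated, which the documents do not show. If they are simple proportions, a Kaplan-Meier figure alone would be a mismatch.

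Finally, a reader might infer that the bias falls where re-operations for non-union cluster. Section 2.7 calls device migration or failure and pseudoarthrosis long-term risks, but no passage gives the timing of re-interventions, and the calculation above assumes a constant hazard.

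**Conclusion.** The point holds in conditional form. Safety rates are assigned to the all-enrolled set at each interval, with no rule for unequal follow-up. Read in the most natural way, this lowers the later re-intervention and SAE rates. With 15% attrition, the shortfall is about 8% in relative terms at 24 months and about 11% for the 12–24 month interval, or under 1 percentage point at a true 24-month risk of 10%.

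The size rests on assumed event rates, constant hazards, independent drop-out, and the VAS attrition figure applying to event follow-up. It is not evidence that biased rates are planned, and no pre-specified decision would change. It is a worthwhile, inexpensive improvement to a primary safety result.

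A separate matter is that enrolment dates from consent, so eligible subjects who are never operated on might also remain in the denominator. The documents give no number for this, and loss of follow-up time would remain after restriction to operated subjects.

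**What to change.** In Section 12.6:

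- For revision, removal, reoperation, supplemental fixation and SAEs, report Kaplan-Meier cumulative incidence from the date of surgery, with 95% confidence intervals at 3, 6, 12 and 24 months, censoring at last contact. Treat death as a competing event for the re-intervention outcomes, using the cumulative incidence function if any deaths occur; for SAEs, death is itself an event under Section 9.1.2.
- In the interval tables, use and display the number of subjects still under follow-up at the start of the interval, and say whether each rate is cumulative or interval-specific.
- Keep the simple proportion alongside, with its denominator stated, because the literature figures may be simple proportions.
- Confirm that event dates and last-contact dates are captured. Section 8.3.1 collects the surgery date and Sections 8.9 and 8.10 require a Study Exit form, but the forms themselves are not in the text reviewed.

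The cost is a few lines of SAP text, one standard added analysis and slightly less favourable rates. Kaplan-Meier does not cure drop-out related to complications, so reasons for exit should be tabulated with the estimates.
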